11.5.2.3. Screening Definitions

The screening value for an assessment is defined as the last non-missing value assessed on or before the screening visit date. For creatinine, eGFR and HbA1c, if both local and Central Lab results are available for a given date then the Central lab value will be used.

11.5.3. Reporting Process & Standards

General

Key efficacy tables will be generated according to current therapeutic area cardiovascular endpoint statistical display standards; otherwise, reporting will be done generally based on the current GSK Integrated Data Standards Library (IDSL) with some variations implemented so as to gain efficiencies from the use of standard PPD programming tools. All analyses will be conducted using SAS Version 9.2 or higher. In general, listings will be sorted by treatment group (arm), site ID, and unique subject ID. If no data are available for a table, listing, or figure then the text "No Data to Report" will be printed in the body of the display. All outputs will be provided by PPD as portable document format (PDF) files; also rich text format (RTF) files will be provided for tables and listings. SDTM version 3.1.3, Analysis Data Model (ADaM) version 2.1 and ADaM IG v1.0 will be used for datasets.

11.5.4. Laboratory Assessments

Censored Laboratory Assessments

Laboratory results that are beyond the limits of quantification will have the inequality sign dropped ($<$, \leq, $>$, \geq, 'less than', 'greater than', or text equivalents) and the quantification limit will be used as the numeric result for summarization.

11.5.5. Adverse Events Conventions

Adverse Events	
AE Onset Time Since First Dose (Days)	
 • If Treatment Start Date $>$ AE Onset Date : = AE Onset Date - Treatment Start Date • If Treatment Start Date \leq AE Onset Date : = AE Onset Date - Treatment Start Date + 1 • Missing otherwise
AE Duration (Days)	
 • AE Resolution Date – AE Onset Date + 1
AE = Drug-related	
 • If relationship is marked 'YES' on eCRF OR value is missing.

11.5.6. Coding of Adverse Events and Medications

Medications
Medications collected on the concomitant medication eCRF screen will be coded using the GSK Drug coding dictionary and summarized by GSK-Drug Anatomical Therapeutic Chemical (ATC) classification level 1 (body system).
Adverse Events
Adverse events will be coded using the Medical Dictionary for Regulatory Activities (MedDRA).

11.6. Appendix 6: Derived and Transformed Data

11.6.1. General

Multiple Measurements at One Time Point

- If there are multiple valid records for an assessment within an assigned analysis visit (i.e., assigned by site and/or assigned by slotting), only one of these records will be used for summary statistics and analyses. The record to be used is determined using the following hierarchy (in decreasing order):
 - the record closest to the target visit day
 - the record with an original nominal visit that matches the analysis visit
 - the record earliest in time
 - if the above does not result in a unique record, then the maximum assessment value of the records identified will be used in the determination of summary statistics
- Regardless of the determination of the record to be used for summary statistics, if data are listed, all data will be presented.
- Subjects having both High and Low values for Normal Ranges at any post-baseline visits for safety parameters will be counted in both the High and Low categories of “Any visit post-baseline” row of related summary tables. This will also be applicable to relevant Potential Clinical Importance summary tables.

Randomization Date

- Date subject was randomized as recorded in the eCRF.

Treatment Start Date

- First IP start date

Study Completion/Withdrawal Date

- Date of subject completion or withdrawal is recorded in the eCRF and corresponds to the date of withdrawal for subjects withdrawing from study (date at which the investigator agreed, or determined, that the subject's participation in the study was over; typically, this will be last study visit date) or date of completion of study (last study visit date) for subjects who complete the study (per Section 11.7.1). Subjects who die while on study are considered to have completed the study and completion date is the date of death. For subjects lost to follow-up, the date of withdrawal corresponds to the last contact between the Investigator and the subject during the study period as defined in the protocol.

Treatment Stop Date

 • Last IP stop date if complete date (day, month and year) is available • If Last IP Stop date is completely missing and the subject has a non-missing treatment start date, then use the earliest of the following two items: 
 • date of death, • latest of the following four items: 
 ○ last visit date (exclude 5 week post-IP telephone call date), ○ last date of most recent IP injection from the Investigational Product injection site reaction eCRF, ○ last date of last study treatment dose from Liver pharmacokinetic (PK) eCRF, ○ earlier of (date of study completion/withdrawal, last IP start date (if not treatment start date) + 20 weeks). • If Last IP stop date is partial (i.e., either only year, or month and year are nonmissing) then impute as the latest date on or before the earliest of the following two items: 
 • date of death • latest of the following three items: 
 ○ last visit date (exclude 5 week post-IP telephone call date) ○ last date of most recent IP injection from the Investigational Product injection site reaction eCRF, ○ last date of last study treatment dose from Liver PK eCRF that is consistent with the nonmissing date components.
Study Day

 • Calculated as the number of days from randomization date: 
 • Ref Date = Missing → Study Day = Missing • Ref Date < Randomization Date → Study Day = Ref Date – Randomization Date • Ref Date ≥ Randomization Date → Study Day = Ref Date – (Randomization Date) + 1
Treatment Day

 • Calculated as the number of days from treatment start date: 
 • Treatment Start Date = Missing → Treatment Day = Missing • Ref Date < Treatment Start Date → Treatment Day = Ref Date – Treatment Start Date • Ref Date ≥ Treatment Start Date → Treatment Day = Ref Date – (Treatment Start Date) + 1
Last CV Assessment Date

 • Last CV Assessment Date is the latest visit date on or before the date of the End of Study visit (clinic visit, telephone call, other contact, 3rd party contact) where all elements of the primary endpoint are captured (i.e., for which the Cardiac Ischemic Event event status and the Stroke/TIA event status are marked as “Yes” or “No”). For subjects who complete the study on treatment, the 5 week post IP telephone call will not be included. For subjects who have withdrawn consent for all follow-up, the Last CV Assessment Date is considered to be the date of withdrawal of consent or the Last CV Assessment, whichever occurs earlier.

Last Study Contact Date

 Last study contact date (clinic visit, telephone or video contact or other contact with the subject or contact with party other than the subject) is the date of last point of study follow-up at which vital status is known. For subjects who have withdrawn consent for all follow-up the last study contact date will include all follow-up where vital status has been established (e.g. via publicly available sources) after the date of withdrawal of consent.
Time Definitions (per GSK standard principles)

 1 week = 7 days 1 month = 30.4375 days 1 year = 365.25 days

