11.3. Appendix 3: Assessment Windows

11.3.1. Assessment Windows

Data will be analyzed based on the visit information recorded in the eCRF. Data for unscheduled visits (including AESI labs and vitals and also CV event vitals), final study clinic (i.e., End of Study) visits (those scheduled to occur within the 3 month window), follow-up phone calls (5 ± 1 weeks after last IP dose) and early withdrawal visits will be assigned to a scheduled visit if the visit date falls within the corresponding protocol-defined visit window (Section 11.2) as specified. For lab data other than lipids the assignment to post-baseline visits will only be done for Central lab data (local lab data will be excluded).

Scheduled Visit	Target Study Day of Visit	Slotting Intervals
Screening	Not applicable	Not applicable
Randomization/Baseline	1	Not applicable
Month X, X=4, 8, 12, 16, etc.	X calendar months after the randomization date. If there is no such date then target is the latest day of that month. For example, if randomization is 31 July then Month 4 target date is 30 November.	Target study day +/- 18 days (inclusive)

Lipid data from local labs are recorded in the Lipids Collection log eCRF. Baseline values will be determined as per Section 11.5.2. Post-baseline values will be assigned in the following manner:

Scheduled Visit	Target Study Day of Visit	Slotting Intervals
Month 12	Month 12 visit date	(treatment start date + 1) to Month 12 visit date (inclusive); if treatment start date is missing then use randomization date instead
Month 24.	Month 24 visit date	(Month 12 visit date + 1) to Month 24 visit date (inclusive)
Month 36, etc.	Analogous to Month 24	Analogous to Month 24

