3.144	Summary of On-therapy Malignant Neoplasms by History of Malignancy at Baseline, SOC, HLT and PT	Safety	SOC, HLT and PT, #/% of subjects and # of events, event density
3.145	Summary of Mantel-Haenszel Analysis of On-therapy Malignant Neoplasms, Stratified by History of Malignancy at Baseline	Safety	
3.146	Summary of On-therapy and Post-therapy Liver Monitoring/Stopping Event Reporting	Safety	
3.147	Summary of On-therapy Hepatobiliary Laboratory Abnormalities	Safety	
3.175	Summary of Liver Function Tests of Potential Clinical Concern	Safety	
3.148	Summary of On-therapy and Post-therapy Other CV Events	Safety	Other CV event category, #/% of subjects and # of events, event density
3.149	Summary of On-therapy Other CV Events	Safety	Other CV event category, #/% of subjects and # of events, event density
3.150	Summary of Chemistry Values	Safety	
3.151	Summary of Change from Baseline Chemistry Values	Safety	
3.152	Summary of Chemistry Values of Potential Clinical Concern	Safety	
3.153	Summary of Change from Baseline Creatinine Values of Potential Clinical Concern by Baseline eGFR	Safety	baseline eGFR category (Normal \geq 90, Mild \geq 60 to $<$ 90, Moderate \geq 30 to $<$ 60, and Severe $<$ 30 ml/min/1.73m ²)

Table No.	Title	Population	Programming note
3.154	Summary of Chemistry Shifts From Baseline with Respect to Potential Clinical Concern	Safety	
3.155	Summary of Change from Baseline Creatinine Values of Potential Clinical Concern (Central Laboratory Data) by Baseline eGFR	Safety	baseline eGFR category (Normal ≥ 90 , Mild ≥ 60 to < 90 , Moderate ≥ 30 to < 60 , and Severe < 30 ml/min/1.73m ²)
3.156	Summary of eGFR	Safety	Only use computed values
3.157	Summary of Change From Baseline in eGFR	Safety	Only use computed values
3.158	Summary of MMRM Analysis for On-treatment eGFR (ml/min/1.73m ²) Change From Baseline (Baseline Data from Local or Central Laboratory, and Post-baseline Central Laboratory Data)	Safety	Only use computed values
3.159	Summary of MMRM Analysis for On-treatment eGFR (ml/min/1.73m ²) Change From Baseline (Central Laboratory Data)	Safety	Only use computed values
3.160	Summary of eGFR Categories	Safety	Only use computed values
3.161	Summary of Shifts from Baseline in eGFR	Safety	Only use computed values
3.162	Summary of Shifts from Baseline in eGFR (Central Laboratory Data)	Safety	Only use computed values
3.163	Summary of Vital Signs	Safety	BP and Heart Rate
3.164	Summary of Change From Baseline Vital Signs	Safety	BP and Heart Rate

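### The one-record-per-visit rule and ±18-day slotting have no worst-value exception for the safety-threshold displays, so ever-abnormal counts can be understated

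*SAP*

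**What the plan says.** **Record selection (SAP Section 11.6.1, Multiple Measurements at One Time Point).** Where one analysis visit holds several valid records, "only one of these records will be used for summary statistics and analyses". The first criterion is "the record closest to the target visit day". Next come a matching nominal visit and then the earliest record. Severity enters only if all of these tie: "then the maximum assessment value of the records identified will be used in the determination of summary statistics". The one exception in the block is for listings: "if data are listed, all data will be presented".

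**Threshold tables (same block).** A subject with both High and Low values across post-baseline visits is counted in both categories of the any-visit post-baseline row. The SAP adds: "This will also be applicable to relevant Potential Clinical Importance summary tables". It does not say whether records that were not slotted, or not selected, feed that row.

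**Slotting (Section 11.3.1).** Unscheduled data, expressly including laboratory and vital-sign records from adverse events of special interest and vital signs from CV events, "will be assigned to a scheduled visit if the visit date falls within the corresponding protocol-defined visit window". The window is 18 days either side of a target every 4 months. Apart from lipids, post-baseline laboratory assignment is confined to Central-laboratory results.

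**Displays concerned (Section 11.15.6).** Tables 3.152 and 3.154 (chemistry values and shifts by clinical concern), 3.165 to 3.167 (vital signs) and 3.175, "Summary of Liver Function Tests of Potential Clinical Concern". The thresholds in Section 11.8 reach 10 times the upper limit of normal (ULN) for ALT, AST and bilirubin. Table 3.175 carries no selection rule of its own.

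**Renal displays.** Section 8.2.2 bases eGFR summaries on scheduled-visit values, and the same paragraph plans the shift to the most severe post-baseline category. Section 9.2.1 limits creatinine summaries to post-baseline scheduled-visit Central-laboratory data.

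**The concern.** Choosing the record nearest the target day suits a by-visit mean or an MMRM, where each subject should contribute one comparable value per visit. A threshold table asks something else: did this subject ever cross the limit? Date proximity has no bearing on that, and ranking it above severity works against the purpose of the table.

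The point has practical weight because Section 11.2.1 schedules liver tests, creatinine and the physical examination only every 8 months. An abnormality that appears and resolves between those visits can reach the database only through an unscheduled record, and those are the records at risk of not being counted.

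At stake are the counts of subjects ever beyond a liver or vital-sign limit, the worst-category eGFR shift, and agreement between the outputs. Listings 23 and 24 show all records for subjects with abnormalities of potential clinical concern. A subject could therefore appear there with a marked ALT elevation and be missing from the matching row of Table 3.175. Figures 3.17 and 3.18 plot maxima without naming their record source. If they use all records they may disagree with the table; if they use selected records they share its understatement.

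**Working it through.** The SAP states no count or rate for this point, so there is no planned figure to reproduce. The check has three parts.

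**1. Two illustrative cases under the literal rules.** Take an ALT of 8 times ULN on an unscheduled Central-laboratory sample.

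| Case | Timing | Slotting (11.3.1) | Selection (11.6.1) | Result |
|---|---|---|---|---|
| A | 15 days from the Month 8 target; a normal routine ALT on the target day | 15 ≤ 18, so Month 8 | Routine value is closer (0 versus 15 days) | Listed; normal value used for the visit |
| B | 40 days after the Month 8 target | 40 > 18, and 121.75 − 40 = 81.75 > 18 from Month 12, so no visit | Not reached | Listed; belongs to no visit |

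If the any-visit row is built from visit-level values, neither case is counted.

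**2. Direction.** Let S be the set of all valid records for a subject and S′ the subset kept. Then max(S′) ≤ max(S) and min(S′) ≥ min(S). The number of subjects ever above, or ever below, a limit can therefore only fall or stay the same. This holds within each arm. It does not fix the direction of any effect on the difference between arms. The last tie-breaker, the maximum, also works against low values such as low blood pressure.

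**3. Window coverage.** Inputs: ±18 days inclusive and 4-monthly targets (11.3.1); 30.4375 days per month and 365.25 per year (11.6.1); liver tests and creatinine at Months 8, 16, 24 and so on (11.2.1); median follow-up of at least 1.5 years (3.2).

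- Window width: 18 + 1 + 18 = 37 days.
- Spacing: 4 × 30.4375 = 121.75 days. Coverage: 37 / 121.75 = 30.4%; outside: 69.6%.
- Over 1.5 years: 1.5 × 365.25 = 547.9 days, with windows at Months 4, 8, 12 and 16. Coverage: 4 × 37 / 547.9 = 148 / 547.9 = 27.0%; outside: 73.0%.

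Inside a window the outcome depends on whether a routine record competes. At Months 4 and 12 no routine liver test or creatinine is scheduled, so a lone unscheduled value is used. Those two windows cover 74 / 547.9 = 13.5% of the time, and Months 8 and 16 cover another 13.5%. A simulation of 1,000,000 uniformly timed unscheduled records gave, where a routine record competes:

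| Assumed deviation of the routine visit from target | Unscheduled record kept | Overall share used |
|---|---|---|
| Uniform over ±18 days | 48% | 13.5% + 13.5% × 0.48 ≈ 20% |
| SD 7 days, limited to ±18 | 27% | 13.5% + 13.5% × 0.27 ≈ 17% |

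These are shares of samples under assumed timing, not shares of subjects missed.

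**The case against.** The strongest reply is that the SAP never says what a reader might infer, namely that the visit rules govern the threshold tables and that abnormal values are thrown away. The one-record rule concerns records already within an assigned visit. Section 11.3.1 says when an unscheduled record joins a visit, not that one which joins none is barred from ever-abnormal counts. The source of the any-visit row is simply undefined. This stands for liver tests and vital signs: the defect is a gap whose literal reading understates, not an express instruction. Nor are values lost, since listings keep them.

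Second, other displays look at the same risk: Table 3.147 and Listing 67 on hepatobiliary criteria, Table 3.146 on liver monitoring and stopping events, the special-interest tables for hepatic events and enzyme elevations, Figures 3.17 and 3.18, and narratives. It would also be wrong to infer that renal deterioration has no event form: Section 11.6.3 lists worsening renal function among the events with specific eCRF details. This stands too. However, event forms and coded terms do not replace counts of measured values against a limit, and the record source of the maxima is not given.

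Third, for creatinine and eGFR the restriction comes mainly from Sections 8.2.2 and 9.2.1. The counts at 1.5 and 2 times baseline are defined by visit, where slotting is appropriate. This also stands. Keeping to one laboratory is a defensible choice, and nothing here requires pooling local results with different assays and reference limits.

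Fourth, the 70% figure assumes uniform timing and counts samples, so it does not measure bias in any table. That is correct.

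**Conclusion.** The point holds as a gap in specification with a known direction. The rules are worded for all summaries, rank date proximity above severity and exempt only listings. Read literally, they can leave an abnormal ALT, AST, bilirubin, blood pressure or heart rate uncounted in Tables 3.152, 3.154, 3.165-3.167 and 3.175. For eGFR, Section 8.2.2 limits the most-severe-category shift to scheduled-visit values more directly. Under that reading the ever-abnormal counts in each arm can only be too low or unchanged.

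The size cannot be derived from the SAP, which gives neither the frequency nor the timing of unscheduled samples. About 70% to 73% of samples would fall outside every window, and 17% to 20% would be used, only under uniform timing and the assumed visit deviations above. A reader might infer that a similar share of affected subjects would be missed, or that a difference between arms would be diluted. The document supports neither inference. The primary MACE analysis is untouched.

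**What to change.** Add one paragraph to Section 11.6.1, before unblinding, that separates two uses of the data:

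- **By-visit means, by-visit counts and MMRM:** keep slotting and the one-record rule as written, including for the by-visit creatinine counts.
- **Any-visit post-baseline, liver-threshold, hepatobiliary and worst-shift rows:** use the worst value in each direction (highest and lowest) over all valid post-baseline Central-laboratory and vital-sign records, scheduled or unscheduled, slotted or not.

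Align Section 8.2.2 with this for the most-severe eGFR shift, and name the record source of Figures 3.17 and 3.18 so that tables, figures and Listings 23 and 24 reconcile. Retain the planned creatinine-assay sensitivity exclusion. Worst-value rows pick up artificially high results more readily, and the four planned reruns in Section 9.2.1 do not include the eGFR shift tables, so a note there would help.

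The cost is SAP wording and a maximum/minimum derivation, with no new data collection. The downside is that unscheduled tests are likely to be done more often in ill subjects, so these rows will not be comparable with the by-visit rows. A footnote on each display should say so.

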- Individual = Represents FL related to any displays of individual subject observed raw data.

[1] On-treatment = first dose of study treatment to last dose of study treatment

[2] On-therapy = first dose of study treatment to last dose of study treatment + 56 days

[3] Subgroups are specified in Section [11.10](#)

[4] Number of Adjudicated MACE, MI, Stroke events

[5] Events during and after defined follow-up periods

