
 The analysis will be based on events positively adjudicated by the CEC and will use the CEC adjudicated event onset dates. First occurrence of adjudicated MACE for a subject is defined as the first adjudicated event, determined by the event date, that is indicated as CV death, MI or stroke. Further details

Primary Statistical Analyses

regarding definitions of events, time to event and time period are provided in Section [11.6.4](#).

- Deaths for which the CEC is unable to establish cause (undetermined cause) will be analyzed as CV deaths except for Analysis Excluding Unknown Cause of Death.
- For subjects who withdraw consent for all follow-up, events occurring up to the date of consent withdrawal will be included in the primary analysis of MACE (i.e. deaths and events collected via publicly available sources subsequent to withdrawal of consent will not be included in the primary analysis but rather in a sensitivity analysis of the primary endpoint).
- Fatal events which are adjudicated to be due to a CV cause, may also have a corresponding CV event adjudicated to determine whether specific endpoint criteria were met (e.g. MI, stroke, heart failure (HF)). Therefore, there may be two adjudication reports for the same fatal CV event. Also, it is possible, for example, that an adjudicated CV death with cause = MI may not meet the adjudication criteria required for MI; and similarly for other fatal events.

Sensitivity and Supportive Statistical Analyses

- As sensitivity analyses, the primary analysis will be repeated based on the On-treatment period (first dose of study treatment to last dose of study treatment) and also based on the On-therapy period (first dose of study treatment to last dose of study treatment + 56 days) using the ITT population, censoring subjects not receiving study treatment at date of randomization.
- A Per-Protocol sensitivity analysis of the primary endpoint will be conducted including all randomized subjects who provide consent and receive at least one dose of study treatment, excluding data after the date of last dose of study treatment + 56 days, and excluding data via censoring for subjects experiencing specified conditions (corresponding definitions are provided in Section [11.1](#)). The Per-Protocol analysis can be viewed as an extension of the On-therapy analysis that in addition accounts for specified conditions.

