For purposes of evaluating criterion 05 only, cases in which partial or missing stop dates are present will be handled as follows:

- Partial or missing last stop date will be imputed as specified for Treatment Stop Date in Section 11.6.1.
- Partial or missing stop dates other than last stop date will be handled as follows:
 - If imputing the earliest possible stop date consistent with the corresponding start date and subsequent start date results in days off study treatment < 56 days then do not exclude data. Otherwise handle as follows:
 - If only year is available, or if date is completely missing, then do not impute stop date and do not exclude data.
 - If month and year are available, but the day of month is missing, then determine the range of potential date values and use the middle of this range as the imputed stop date. The beginning of the potential range of date values is the maximum of the following two dates: start date + 1, the first of the month of the stop date of interest. The end of the potential range of date values is the last day of the month of the stop date of interest. If there is an even number of dates ($n=2m$) in the potential range of date values then use the date corresponding to the $(m+1)$ th of the ordered dates.

For purposes of evaluating criterion 05 only, cases in which partial or missing start dates are present will be handled as follows:

- Partial or missing start dates will be handled as follows:
 - If imputing the latest possible start date consistent with the corresponding stop date and previous stop date results in days off study treatment < 56 days then do not exclude data.
 - If imputing the earliest possible start date consistent with the corresponding stop date and previous stop date results in days off study treatment ≥ 56 days then exclude data based on the earliest possible start date.
 - Otherwise handle as follows:
 - If only year is available, or if date is completely missing, then do not impute start date and do not exclude data.

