Assessment of MACE and micro-vascular events	X		X	X	X
HbA1c	X			X	X
Serum creatinine (eGFR)	X			X	X
Liver Function Tests (LFTs) ⁵	X			X	X
Record available information on most recent lipid assessment ⁶	X		X (annually)	X (annually)	X
Patient reported outcomes questionnaire ⁷	X				
Key concomitant non-diabetes medication	X	X	X	X	X
Diabetes medication	X	X	X	X	X
Physical examination ⁸	X			X	X
AEs leading to IP discontinuation	X				
SAEs, AEs of special interest,	X	X	X	X	X
Study drug compliance	X				

1. After subjects permanently discontinue IP, follow-up should continue on the 4-monthly schedule established at randomization.
2. Where a subject would have been scheduled to attend clinic at months 4, 12, 20, 28 etc after randomization, a telephone contact will be performed instead (with assessments as shown above).
3. Where a subject would have been scheduled to attend clinic at months 8, 16, 24, 32 etc after randomization, a clinic visit will be performed (with assessments as shown above).
If a subject who has permanently discontinued IP is unable to attend clinic then they will be contacted by telephone instead and the telephone contact assessments will be performed.
4. Once it is projected that the target number of MACE events will have been collected, a 3 month window will be defined for conducting the final, face to face visit.
5. Liver function tests: ALT, AST, alkaline phosphatase, bilirubin, GGT.
6. Lipid values (TC, LDLc, HDLc, Tg) to be recorded as available from routine clinical care annually. If results are unavailable, lipids tests are not to be performed for the study.
7. TRIM-D, EQ-5D and study specific questionnaire (details in Protocol Section 6.3).
8. See Protocol Section 6.2.7.

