11.7. Appendix 7: Premature Withdrawals & Handling of Missing Data

11.7.1. Premature Withdrawals

Element	Reporting Detail
General	
 Subject study completion (i.e. as specified in the protocol) was defined as completion of all periods of the study up to and including any follow-up period. Follow-up period here refers to continuing follow-up for CV events (i.e. not the 5 week follow-up visit post IP discontinuation). Withdrawn subjects will not be replaced in the study. All available data from subjects who were withdrawn from the study will be listed and all available planned data will be included in summary tables and figures, unless otherwise specified. Per protocol, subjects may prematurely discontinue study drug but are encouraged to remain in the study.

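### A wholly missing IP stop date is imputed as the last visit or later even for subjects who stopped drug early, so off-drug time counts as on-drug in the supportive analyses

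*SAP*

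**What the plan says.** SAP Section 11.6.1 (Treatment Stop Date) applies the rule as follows: "If Last IP Stop date is completely missing and the subject has a non-missing treatment start date". The imputed date is the earlier of the date of death and the latest of four items:

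- "last visit date (exclude 5 week post-IP telephone call date";
- the last injection date on the injection-site-reaction form;
- the last dose date on the liver PK form;
- "earlier of (date of study completion/withdrawal, last IP start date (if not treatment start date) + 20 weeks".

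A separate branch handles partial dates. It takes the latest date that agrees with the recorded year, or month and year, and is not after death or the latest of the first three items.

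Stopping drug without leaving the study is expected. Section 11.7.1: "Per protocol, subjects may prematurely discontinue study drug but are encouraged to remain in the study". The table for discontinued subjects in Section 11.2.2 adds: "After subjects permanently discontinue IP, follow-up should continue on the 4-monthly schedule established at randomization", and it ends with a final study clinic visit.

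The treatment stop date defines the three analyses that Table 5 lists as key sensitivity analyses of MACE:

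- On-treatment (Section 7.1.2): "On-treatment period (first dose of study treatment to last dose of study treatment".
- On-therapy (Section 7.1.1): "On-therapy = first dose of study treatment to last dose of study treatment + 56 days".
- Per-Protocol, for criterion 05 (Section 11.1.2): "Partial or missing last stop date will be imputed as specified for Treatment Stop Date in Section 11.6.1".

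**The concern.** The last visit is a sensible default for someone still injecting. It is not sensible for someone who has stopped, because that person's visits continue to study end. The rule leaves out the 5-week call, which falls after treatment, but keeps every later post-drug contact. The 20-week item looks like a cap, but it sits inside the latest-of list, so it can lengthen the imputed treatment period and can never shorten it.

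The On-treatment, On-therapy and Per-Protocol analyses show whether the non-inferiority result depends on time spent off drug. If off-drug time is put back into all three by the same imputed date, their agreement with each other and with the ITT result says less than it appears to.

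**Working it through.** **1. The plan's own design figure.** Schoenfeld's formula with margin 1.3, true hazard ratio 1.0, two-sided alpha 0.05, 90% power and 1:1 allocation gives 4 × (1.960 + 1.282)² / (ln 1.3)² = 611 events, as stated. This figure is not in question.

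**2. The rule as a formula.** Stop = min(death, max(last visit, injection-site date, liver PK date, min(completion or withdrawal, last IP start + 140 days))). Because the last visit is inside the max, the result cannot precede it unless death does.

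**3. An illustrative subject** (assumed dates, start on day 1): last dose day 120, last IP start day 50, alive, final visit and completion day 548 (1.5 years, the minimum projected median follow-up), stop date blank.

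- 20-week item: min(548, 50 + 140) = 190.
- Imputed stop: max(548, 190) = 548, against a true 120.

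| Quantity | True stop | Imputed stop | Excess |
|---|---|---|---|
| On-treatment window ends (day) | 120 | 548 | 428 |
| On-therapy window ends, min(stop + 56, 548) | 176 | 548 | 372 |
| Exposure including breaks, (stop + 56)/365.25 (person-years) | 0.48 | 1.65 | 1.17 |
| Expected pens, ceiling(stop/7) | 18 | 79 | 61 |

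If this subject used all 18 pens up to day 120, compliance including breaks would be 18/79 = 23% instead of 100%. For true last doses on days 60, 240 and 365 the On-treatment excess is 488, 308 and 183 days.

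**4. Per-Protocol.** One part of criterion 05 removes data from treatment stop + 57 days. With an imputed stop on day 548 it removes nothing. The part that acts on earlier gaps of at least 56 days still works, as do criteria 03 and 04.

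**5. On-therapy AEs.** Section 11.6.3 ends the window at the earlier of stop + 56 days and latest contact, so person-time grows by the same 372 days. AEs in that time are counted too, so the direction of the effect on a rate is not fixed.

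**6. Partial dates.** With month and year known, the imputed date stays in that month. With only the year known, it is the last date in that year on or before the last visit, so a January stop can become 31 December.

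**7. Possible size.** The SAP does not give the number of wholly missing dates. Assume 0.5–2% of 9400 (47–188 subjects), each with 12 months of later follow-up wrongly counted, and 9400 × 1.5 = 14,100 person-years in total.

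- Misplaced person-time: 47–188 person-years, or 0.33–1.33% of 14,100.
- MACE rate: 611/14,100 = 4.33 per 100 person-years.
- Misplaced MACE: 47 × 0.0433 = 2.0 to 188 × 0.0433 = 8.1, over both arms.

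**8. Effect on a non-inferiority check.** Take an on-drug hazard ratio of exactly 1.3 and an off-drug ratio of 1.0, with a fraction f of person-time misclassified. The diluted ratio is h = 1.3(1 − f) + f, and the one-sided error is Φ[(ln 1.3 − ln h) × √(D/4) − 1.96] with D events.

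| f | h | Error, D = 611 | Error, D = 400 |
|---|---|---|---|
| 0 | 1.300 | 0.0250 | 0.0250 |
| 1% | 1.297 | 0.0267 | 0.0264 |
| 2% | 1.294 | 0.0285 | 0.0278 |
| 5% | 1.285 | 0.0346 | 0.0326 |

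At f = 0.33–1.33% with 611 events the error is about 0.0256–0.0273. On-drug person-time is below 14,100, so f would be somewhat higher in these analyses.

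**The case against.** The best defence is that few records should meet the condition. Section 11.2.2 schedules a clinic visit soon after permanent discontinuation, with a compliance check, and a call timed from the last dose, so the site would normally know that date. Section 11.6.2 also uses the Treatment Stop Date rule to censor subjects who did not discontinue, for whom the last visit is reasonable. This stands: the rule is too broad, and the gap it mishandles is probably uncommon.

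Some stronger readings are tempting, but the SAP does not support them:

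- A reader might infer that a subject known to have stopped around month 5 would be treated as dosing to month 24. If month and year are recorded, the partial-date branch keeps the stop in that month. The long error needs a wholly missing date; a year-only date can still be up to most of a year late.
- A reader might infer that the rule favours non-inferiority in general. It does so only if the on-drug hazard ratio is above 1. With a neutral drug there is no pull, and with a beneficial one the dilution works against the sponsor.
- A reader might infer that the primary result or all AE tables are affected. The primary analysis is ITT over the whole CV follow-up period and does not use the stop date. The combined On-therapy and Post-therapy AE tables are not affected either. Section 11.4.2 deliberately assigns AEs to On-therapy when the stop date is missing, which is a defensible conservative choice for counts.
- For exposure and compliance excluding breaks, the text does not say that the imputed date enters.

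None of this answers the central point. When the condition is met, the rule dates the last dose at or near study end for someone known to have stopped earlier.

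**Conclusion.** The concern holds as a minor point. For a subject who permanently discontinued IP, stayed in follow-up and has a wholly missing stop date, Section 11.6.1 gives the last visit or later, capped at death. The On-treatment and On-therapy MACE analyses and the final-stop part of Per-Protocol criterion 05 then move towards the ITT result. That weakens them as a check on non-inferiority if the on-drug hazard ratio exceeds 1. Exposure and compliance including breaks, and On-therapy AE person-time, are also distorted.

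Per subject the error can exceed a year. Across the trial the size is unknown. The 2–8 MACE and the error of 0.0256–0.0273 rest on an assumed share of missing dates, 12 months of later follow-up each and, for the error, a true on-drug hazard ratio of 1.3. No confirmatory decision changes.

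**What to change.** In Section 11.6.1, split the rule by recorded discontinuation status.

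- For subjects recorded as having permanently discontinued IP, impute a wholly missing stop date as the earliest of death, the clinic visit held after permanent discontinuation, and last dispensing date + 20 weeks. Make it no earlier than the last injection documented on the injection-site-reaction or liver PK form.
- Apply the same rule to a year-only date, kept within the recorded year.
- Keep the current last-visit rule for subjects not recorded as discontinued.

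The post-discontinuation visit follows the last dose by definition, so that bound cannot cut off real treatment time. In the illustrative case, if that visit were missing and the last dispensing was on day 50, the imputed stop would be day 190. The error would be 70 days instead of 428.

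The cost is one revised derivation, set before unblinding, from discontinuation, visit and dispensing data that the SAP already uses. A few events and AEs would move from on-drug to off-drug. The Section 11.4.2 convention of assigning AEs to On-therapy can stay for AE counts. The CSR should report, by arm, how many stop dates were imputed under each branch.
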